#### 390 All Registry/Screening Visit testing procedures are considered standard care.

391 The following procedures will be performed and documented (including data collection and  
 392 eligibility criteria checks) at the Registry/Screening Visit:

- 394 1. Inclusion and exclusion criteria assessed
- 395 2. Demographics (date of birth, sex, race, and ethnicity)
- 396 3. Contact information (retained at the site and not entered on the study database)
- 397 4. Collection of MyRetinaTracker Registry ID (if participating and consented to provide)
- 398 5. Medical history – will be elicited from the study participant and extracted from available  
 399 medical records, including patient-reported daily activities, pre-existing medical  
 400 conditions, medications, and audiology history

- 401 6. Concomitant medications
- 402 7. Ophthalmic examination
- 403       ♦ Can be performed within ninety (90) days of the Registry/Screening Visit or a
- 404       historical measurement performed *within the last six (6) months* prior to the
- 405       Registry/Screening Visit.
- 406       ♦ Complete ophthalmic examination to include:
- 407             ♦ Slit lamp biomicroscopy
- 408             ♦ Indirect ophthalmoscopy
- 409 8. Visual acuity (including refraction, ETDRS, BRVT if needed, and LLVA if needed)\*
- 410       ♦ The VA letter score will determine whether LLVA or BRVT will be performed.
- 411       The criteria are defined in the **Uni-Rare Clinical Site Manual of Procedures**.
- 412 9. Intraocular Pressure (IOP)
- 413       ♦ IOP measurements are to be taken prior to pupil dilation.
- 414 10. Spectral Domain Optical Coherence Tomography (SD-OCT)\*
- 415       ♦ Volume Scan
- 416       ♦ Vertical and Horizontal Scan
- 417 11. Static Perimetry (SP)\*
- 418 12. Kinetic Visual Field III4e (Kinetic Perimetry [KP])\*
- 419       ♦ **Vision Cohort 1 and 2:** Historical measurement performed *within the last*
- 420       *eighteen (18) months* prior to the Registry/Screening Visit. If a historical
- 421       measurement is not available, then perform the Kinetic VF III4e during the
- 422       Registry/Screening Visit.
- 423       ♦ **Vision Cohort 3:** Collect the *most recent* historical measurement prior to the
- 424       Registry/Screening Visit, if available. Kinetic VF III4e does not need to be
- 425       performed at screening if a historical measurement is not available.
- 426 13. Determination of Vision Cohort (see section 2.2)

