- 427       ♦ If the participant’s determined Vision Cohort is closed for enrollment, the
- 428       remainder of procedures and testing are not required. Participant will be
- 429       discontinued as an *initial screen failure*.
- 430       ♦ Participants in the Younger Age Cohort will not be assigned to a Vision Cohort.
- 431 14. Genetic screening assessment, including number and phase of mutations in the causal
- 432       gene, history of consanguinity, and collection of the source genetic report(s) available at
- 433       the clinical site.
- 434       ♦ This includes an assessment that the participant meets one of the **Genetic**
- 435       **Screening Criteria**. If the participant does not meet one of these criteria, then the
- 436       remainder of procedures and testing are not required. The participant will be
- 437       discontinued as an *initial screen failure*.
- 438 *\*This testing procedure will not be completed for participants in the Younger Age Cohort.*

439 **2.4.3 Initial Screen Failures**

440 Participants who do not meet criteria to continue as noted above will be discontinued as an *initial*  
 441 *screen failure*. The Screening Visit Form will still be completed, entering “Not Done” for testing  
 442 not finished. A Final Status Form will be completed, and the reason for screen failure will be  
 443 noted.

444 **2.5 Genetic Screening Phase**

445 Participants passing the initial screening and *enrolled into the genetic screening phase* will have  
 446 their genetic lab reports submitted for Central Genetics Auditor (CGA) review. The schematic of  
 447 study design at the beginning of the protocol summarizes the flow of the **Genetic Screening**  
 448 **Phase**. Reference the **Uni-Rare Clinical Site Manual of Procedures** for detailed procedures.

449 All genetic reports will be uploaded to the FFB study website by the clinical site. These reports  
 450 may be reviewed by the CC, associated clinical site, CGA, Genetics Committee, and  
 451 Investigator(s) involved in the oversight of the study (which includes the study chair, Operations  
 452 Committee, and Executive Committee). All genetic reports will be de-identified and redacted of  
 453 all personal data prior to uploading on the FFB study website.

454 The CGA will review the genetic documentation provided by the clinical site to verify the  
 455 genetic screening data entry and appropriate documentation of the **Genetic Screening Criteria**.  

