#### 1116 9.1.1 General Considerations

1117 Both eyes of a participant will be assessed for the main ocular measures of interest. Thus, if there  
1118 are N participants, 2N eyes will be available for analysis. However, outcome measures from two  
1119 (2) eyes of a person are typically strongly correlated ( $r \geq 0.5$ ). The contribution of information  
1120 from the two (2) eyes in this case is  $(2/(1+r))$  instead of two (2). Values for the multiplier to the  
1121 number of participants to obtain an effective sample size are given below in **Table 9-1**. The  
1122 correlation between eyes (inter-eye correlation) for each outcome measure is not known. We  
1123 assume an inter-eye correlation of 0.8 throughout all sample size calculations throughout section  
1124 1.1. This assumption is conservative in that it requires a higher number of participants than lower  
1125 plausible values of r.

1126 **Table 9-1. Multiplier to Obtain Effective N Based on Inter-Eye Correlation**

r	0.0	0.1	0.2	0.3	0.4	0.5	0.6	0.7	0.8	0.9	1.0
Multiplier for Effective N	2.00	1.82	1.67	1.54	1.43	1.33	1.25	1.18	1.11	1.05	1.00

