#### 1132 Registry Objective 2 (Cross-Sectional Phenotype Characterization)

- 1133 ➤ **Registry Objective 2** is to characterize cross-sectional retinal dystrophy associated with  
1134 disease-causing genetic variants using functional and structural measures, **within gene**.
- 1135 ➤ For a given gene, the potential sample size for the gene will impact the precision around  
1136 the point estimates for the key measures of interest.
- 1137 ➤ **Table 9-2, 9-3, and 9-4** provide the half-width of the 95% confidence interval (CI)  
1138 around the estimated cross-sectional mean value, for three key measures of interest  
1139 (visual acuity, OCT EZ area, and SP  $V_{tot}$ , respectively) under different possible sample  
1140 sizes and standard deviations (SD) of the distribution of the cross-sectional measure. The  
1141 larger the SD and/or the smaller the sample size, the wider the CI, meaning the range of  
1142 possible true values grows.

1143 **Table 9-2. Half-Width of 95% Confidence Intervals Around the Estimated Mean Cross-**  
 1144 **Sectional Visual Acuity**

	Sample Size									
	(effective sample size after adjusting for inter-eye correlation r=0.8)									
	N=10	N=20	N=30	N=40	N=50	N=60	N=70	N=80	N=90	N=100
	(11)	(22)	(33)	(44)	(56)	(67)	(78)	(89)	(100)	(111)
SD=5	3.4	2.2	1.8	1.5	1.3	1.2	1.1	1.1	1.0	0.9
SD=10	6.7	4.4	3.5	3.0	2.7	2.4	2.3	2.1	2.0	1.9
SD=15	10.1	6.7	5.3	4.6	4.0	3.7	3.4	3.2	3.0	2.8
SD=20	13.4	8.9	7.1	6.1	5.4	4.9	4.5	4.2	4.0	3.8

1145 Units = letter score

1146 **Table 9-3. Half-Width of 95% Confidence Intervals Around the Estimated Mean Cross-**  
 1147 **Sectional OCT Ellipsoid Zone Area**

	Sample Size									
	(effective sample size after adjusting for inter-eye correlation r=0.8)									
	N=10	N=20	N=30	N=40	N=50	N=60	N=70	N=80	N=90	N=100
	(11)	(22)	(33)	(44)	(56)	(67)	(78)	(89)	(100)	(111)
SD=2	1.3	0.9	0.7	0.6	0.5	0.5	0.5	0.4	0.4	0.4
SD=5	3.4	2.2	1.8	1.5	1.3	1.2	1.1	1.1	1.0	0.9
SD=8	5.4	3.5	2.8	2.4	2.1	2.0	1.8	1.7	1.6	1.5
SD=10	6.7	4.4	3.5	3.0	2.7	2.4	2.3	2.1	2.0	1.9

1148 Units = mm^2

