1149 **Table 9-4. Half-Width of 95% Confidence Intervals Around the Estimated Mean Cross-**  
 1150 **Sectional Static Perimetry Vtot (Hill of Vision)**

	Sample Size									
	(effective sample size after adjusting for inter-eye correlation r=0.8)									
	N=10	N=20	N=30	N=40	N=50	N=60	N=70	N=80	N=90	N=100
	(11)	(22)	(33)	(44)	(56)	(67)	(78)	(89)	(100)	(111)
SD=10	6.7	4.4	3.5	3.0	2.7	2.4	2.3	2.1	2.0	1.9
SD=15	10.1	6.7	5.3	4.6	4.0	3.7	3.4	3.2	3.0	2.8
SD=20	13.4	8.9	7.1	6.1	5.4	4.9	4.5	4.2	4.0	3.8
SD=25	16.8	11.1	8.9	7.6	6.7	6.1	5.6	5.3	5.0	4.7

1151 Units = dB-sr

1152

1153

1154

1155

1156

1157 **Registry Sample Size Example**

1158 The following is an example of using the tables above and a set of assumptions for a given gene  
 1159 of interest to determine the precision of cross-sectional estimates of key measures.

Gene	BBS1	
Anticipated Sample Size	50	
Key Measure	Assumed Standard Deviation (SD)	Precision around estimated mean value (half-width of 95% CI)
Visual Acuity	10	2.7
OCT EZ Area	5	1.3
SP $V_{tot}$	20	5.4

1160 Assumptions based on Mean (standard deviation) of RUSH2A baseline  $V_{tot}$ , VA, and OCT EZ  
 1161 RUSH2A shown below

	Overall	USH2	ARRP
VA	77.9 (11.7)	76.5 (12.4)	80.3 (10.2)
OCT EZ area	3.6 (5.6)	3.1 (5.7)	4.3 (5.6)
SP $V_{tot}$	27.8 (23.7)	22.5 (21.5)	37.1 (24.7)

1162 **9.1.3 Natural History Study Sample Size Considerations**

1163 As noted in section 4.1, the designation of **NHS Target Genes** will be made by the Executive  
 1164 Committee on an ongoing basis and may depend on funding resources as well as Registry  
 1165 enrollment numbers within gene. The Natural History Study sample size for each gene will  
 1166 depend on the Registry enrollment. Since the within-gene Registry limit is 100 participants, this  
 1167 will be the maximum sample size for **NHS Target Genes**.

1168 The following NHS sample size considerations focus on **NHS Objectives 1-3** (see section 1.3).  
 1169 For all of these objectives, the following principles will apply in the sections below:

- 1170 ➤ For simplicity across all measures, **percent change** will be considered for sample size  
 1171 justification purposes.
- 1172 ➤ Also for simplicity, although statistical analyses will include the data from each annual  

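### Does the Registry worked example overstate precision by assuming SDs below every RUSH2A SD printed beneath it?

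*Protocol*

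**What the plan says.** Protocol section 9.1.2 ends with a worked example for one gene, BBS1, listed with "Anticipated Sample Size 50". It is offered as a demonstration of how to use Tables 9-2 to 9-4. The assumed SDs are 10 for visual acuity, 5 for OCT EZ area and 20 for static perimetry V_tot, and the half-widths read off are 2.7, 1.3 and 5.4.

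The note under the example reads "Assumptions based on Mean (standard deviation) of RUSH2A baseline", followed by the three measures and a small table with columns Overall, USH2 and ARRP. It does not say which column was used or how its SDs became 10, 5 and 20.

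The effective sample size comes from section 9.1.1, where the authors "assume an inter-eye correlation of 0.8 throughout all sample size calculations". The same section says that if there "are N participants, 2N eyes will be available for analysis". In section 2.4.2, visual acuity, SD-OCT and static perimetry carry the footnote "This testing procedure will not be completed for participants in the Younger Age Cohort".

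**The concern.** An example that cites a source should be traceable to it. Here none of the nine printed SDs equals the assumed value for its measure, and all nine are larger. A smaller SD gives a narrower interval, so every departure flatters the stated precision. Section 4.1 sends readers to chapter 9 for the justification of within-gene sample sizes, so someone planning for another gene may copy the method and carry over the same optimism. The protocol elsewhere describes its planning choices as conservative (the inter-eye correlation in 9.1.1, the simplified change measure in 9.1.3), and this one runs the other way.

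A second, smaller worry concerns the count of eyes. Children in the Younger Age Cohort do not have the three measures taken at the Registry visit. If they were counted in the N of Tables 9-2 to 9-4, they would supply no eyes, and the tabled precision would be too good for a gene with many such children.

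**Working it through.** **Inputs.** N = 50; inter-eye correlation r = 0.8 (section 9.1.1); assumed SDs 10/5/20; RUSH2A SDs from the table under the example.

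**Reproducing the stated figures.** The multiplier is 2/(1 + 0.8) = 1.11, so effective n = 50 × 1.11 = 55.6, printed as 56. The half-width is t(0.975; 55) × SD/√56 = 2.004 × SD/7.483 = 0.2678 × SD.

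- Visual acuity: 0.2678 × 10 = 2.68
- EZ area: 0.2678 × 5 = 1.34
- V_tot: 0.2678 × 20 = 5.36

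These round to 2.7, 1.3 and 5.4, so the example's arithmetic is right. A normal quantile would give 2.62, 1.31 and 5.24, so the tables use the t quantile.

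**With the printed SDs.** At fixed N the half-width is proportional to the SD.

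| Measure (assumed SD, half-width) | Overall | USH2 | ARRP |
|---|---|---|---|
| VA (10, 2.68) | 11.7 → 3.13 (+17%) | 12.4 → 3.32 (+24%) | 10.2 → 2.73 (+2%) |
| EZ area (5, 1.34) | 5.6 → 1.50 (+12%) | 5.7 → 1.53 (+14%) | 5.6 → 1.50 (+12%) |
| V_tot (20, 5.36) | 23.7 → 6.35 (+18.5%) | 21.5 → 5.76 (+7.5%) | 24.7 → 6.61 (+23.5%) |

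In absolute terms the gaps are about 0.05 to 0.64 letters, 0.16 to 0.19 mm² and 0.40 to 1.26 dB-sr.

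**Where 10/5/20 can come from.** Tables 9-2 to 9-4 offer only these SD rows: 5, 10, 15, 20 (VA); 2, 5, 8, 10 (EZ area); 10, 15, 20, 25 (V_tot). A lookup has to choose a row.

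- VA: 11.7, 12.4 and 10.2 are all nearest to 10. USH2 is close to the midpoint: 12.4 lies 2.4 from 10 and 2.6 from 15.
- EZ area: 5.6 and 5.7 are nearest to 5.
- V_tot: 21.5 is nearest to 20; 23.7 and 24.7 are nearest to 25.

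Seven of the nine printed SDs therefore lead to the row used, and the USH2 column gives 10/5/20 exactly. Overall and ARRP each give 10/5/25, and at N = 50 Table 9-4 shows 6.7 for SD 25.

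**Cross-check within the chapter.** The Natural History Study example in section 9.1.3 prints RUSH2A SDs of 5.1%, 21.8% and 28.2% and assumes 5%, 20% and 30%. Each is the nearest row of Table 9-5, and the last is rounded up. Nearest-row rounding fits both examples, and it does not always favour precision.

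**What depends on the result.** The 1,500 total, the within-gene cap of 100 and the thresholds of 20 and 40 for the within-gene objectives are not derived from this example. The figure of 50 is an anticipated number, not the solution to a precision target, so converting the wider half-widths into a larger required N would answer a question the protocol does not ask.

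**Younger Age Cohort.** The tables give the precision of a mean over a stated number of participants. A child without a measurement does not enter that mean, so the natural N is the number who have the measure. The BBS1 example does not say that such children are among its 50, and the documents give no expected number from which to size an effect.

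**The case for a change.** The strongest case for a change is that the reader cannot tell which adjustment was made. The wording allows the assumptions to differ from the source, but it should let a reader retrace them. The section 9.1.3 example can be retraced because it prints one set of SDs; this one prints three and picks none. If USH2 was the source, all three SDs were rounded down, and visual acuity only just falls to the lower row. If Overall was the source, which is a reasonable default, the protocol's own table gives 6.7 for V_tot and not 5.4. The repair would cost a sentence and at most three figures.

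The facts in this stand: the column and the rounding are not stated, and V_tot is ambiguous. The inference that the plan is harmed does not. The source SDs are printed directly below the example, the tables show the next rows up at N = 50 (4.0 letters, 2.1 mm² and 6.7 dB-sr), and section 9.1.2 itself warns that a larger SD widens the interval. RUSH2A is also a stand-in: the documents give no SD for BBS1, so half-widths from 11.7, 5.6 and 23.7 show sensitivity to a proxy and are not corrected values for that gene.

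**Conclusion.** No change is needed. The stated half-widths are correct for the SDs assumed, and those SDs match the USH2 column rounded to the nearest table row. What remains is an unstated convention in an illustrative example. Taken at face value it makes the example's half-widths 2% to 24% narrower than the printed SDs would give. If Overall or ARRP was intended, V_tot would read 6.7 from the table, or 6.3 or 6.6 from the actual SDs, in place of 5.4. The Younger Age Cohort wording has no demonstrable size, and an analyst would resolve it by counting participants who have the measure.

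This rests on three readings. The example sets nothing, since no cap, threshold or sample size in the protocol is traced to it. Nearest-row lookup is inferred from the two examples and is not stated. Finally, the intervals eventually reported will use each gene's observed SD and inter-eye correlation, as section 9.2 indicates by adjusting intervals for the correlation between eyes. Naming the column would help a careful reader but would alter no result.

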Vision Cohort 2 Approximately 450 participants	Criteria that must be met in the better eye* at the Registry/Screening Visit: ○ visual acuity ETDRS letter score of 19-53 (approximate Snellen equivalent 20/100 to 20/400) OR

	○ visual acuity ETDRS letter score of 54 or more (approximate Snellen equivalent 20/80 or better) and visual field** diameter less than 10 degrees in any meridian of the central field
Vision Cohort 3 Approximately 150 participants	Criteria that must be met in the better eye* at the Registry/Screening Visit: ○ visual acuity ETDRS letter score of 18 or less (approximate Snellen equivalent 20/500 or worse)
*Better Eye	The better eye is defined as the eye with the better Registry/Screening Visit ETDRS visual acuity. However, if both eyes have the same visual acuity, which is defined as the same Snellen equivalent, then the determination will be made at the Investigator’s discretion. In this scenario, the Investigator will consider the eye with better fixation or clearer ocular media to permit highest quality retinal imaging.
**Visual Field	The visual field (VF) is defined as the clinically determined kinetic VF III4e performed within the last 18 months prior to the Registry/Screening Visit or performed on the day of the Registry/Screening Visit.

237

238 **Vision Cohort Grid**

	VF diameter <math>\geq 10^\circ</math> in every meridian	VF diameter <math>< 10^\circ</math> in any meridian
20/80 or better	Vision Cohort 1	Vision Cohort 2
20/100-20/400	Vision Cohort 2	Vision Cohort 2
20/500 or worse	Vision Cohort 3	Vision Cohort 3

239

240 **Younger Age Cohort Definition**

Younger Age Cohort	
 
• Participants who are between the ages of <math>\geq 4</math> years and <math>< 8</math> years old will be designated as the Younger Age Cohort.
 
• Participants in this cohort will not be assigned a Vision Cohort.
 
• Registry/Screening Visit and Natural History Study Visits will have an abbreviated testing schedule.
 

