 1262 *40 or more*).
- 1263 ○ Methods will include univariate and multivariate analysis of  
 1264 covariance (ANCOVA) models. A stepwise selection procedure will  
 1265 be used to build the final model. A threshold of  $P < 0.10$  will be used to  
 1266 add to the model, and a threshold of  $P < 0.05$  will be used to remain in  
 1267 the multivariate model. Linearity of continuous factors will be  
 1268 assessed, and possibly quadratic or cubic terms will be considered if  
 1269 non-linear.
- 1270 ○ Potential risk factors to evaluate include:
- 1271     ▪ Phenotypic:
- 1272         • Clinical diagnosis (if applicable)
- 1273         • Duration of disease
- 1274         • Age of onset of initial vision symptoms
- 1275         • Gender
- 1276         • Race/ethnicity
- 1277         • Visual acuity
- 1278         • Lens Status (phakic/pseudophakic/aphakic)
- 1279     ▪ Genotypic:
- 1280         • Characterizations of the variants
- 1281     ▪ Environmental factors
- 1282         • Smoking status
- 1283         • Vitamin A use
- 1284         • Docosahexaenoic acid (DHA) use
- 1285         • Lutein use
- 1286 ○ Variability of symmetry of left and right eye cross-sectional outcome  
 1287 measures will be evaluated by scatterplots. Bland-Altman plots of the inter-  
 1288 eye difference versus the mean value will be inspected and a linear regression  
 1289 model for the differences will be used to test whether the intercept (overall  
 1290 mean difference) and slope is 0. The plot will be inspected to evaluate whether  
 1291 variability between eyes changes with greater mean values. The intraclass  
 1292 correlation coefficient of the values and the within-person variance will be  
 1293 estimated.

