 1364 assessed and the symmetry of the change from baseline from the left and right eyes will be  
 1365 assessed for each follow-up visit. Bland-Altman plots of the inter-eye difference versus the  
 1366 mean value will be inspected. The intraclass correlation coefficient of the values will be  
 1367 estimated.

1368 **2.3 Interim Data Analysis**

1369 No formal interim analysis or “stopping guidelines” are planned for determining early stopping  
 1370 according to statistical rules, as no intervention is being studied and thus early efficacy and  
 1371 safety signals are not applicable.

1372 Interim analyses will be planned for other reasons, including to evaluate data at baseline and  
 1373 annual visits for reporting in preliminary manuscripts, as well as monitoring data for recruitment  
 1374 and retention benchmarks, and quality assurance throughout the duration of the study. The FFB  
 1375 Consortium Executive Committee will review and oversee these data and their use in reporting.

1376

1377

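### Registry inter-eye symmetry (section 9.2.1): the intercept of the difference-on-mean regression is not the overall mean difference unless the mean is centred

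*Protocol*

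**What the plan says.** The analysis is the last bullet under Registry Objective 2 in protocol section 9.2.1. It calls for scatterplots of right against left eye and for Bland-Altman plots. The inter- "eye difference versus the mean value will be inspected and a linear regression" "model for the differences will be used to test whether the intercept (overall" "mean difference) and slope is 0" (the three fragments are consecutive lines of one sentence). Visual inspection for changing spread, an intraclass correlation and the within-person variance complete the bullet.

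The protocol does not say that the mean value is centred before fitting, or that the mean difference comes from a separate model without a slope. The Natural History Study symmetry analysis (section 9.2.2, Other Planned Analyses) relies on plots and an intraclass correlation and has no such regression: "assessed for each follow-up visit. Bland-Altman plots of the inter-eye difference versus the" mean are inspected, and no intercept is tested.

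**The concern.** The parenthesis treats two different quantities as the same. In a line with a slope, the intercept is the fitted difference where the regressor is 0. Here that means an eye pair averaging 0 letters, 0 mm² of EZ area or 0 dB-sr of V_tot. For visual acuity this is far outside the data: with the RUSH2A mean of 77.9 letters, 0 lies about 7 standard deviations of the inter-eye mean below the centre.

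If the model is fitted as the sentence reads, with separate tests, there are two risks.

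- With a true slope, the intercept test can reject when the eyes do not differ on average, or miss a difference that exists.
- With no slope, the intercept is right in expectation but much too imprecise for visual acuity. A non-significant result could then be reported as no average left-right difference from a test with almost no power.

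Because Objective 2 is a within-gene objective, the same test would be repeated gene by gene.

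**Working it through.** The protocol gives no figure for this analysis, so there is none to reproduce. The check is the algebra, followed by its size under the protocol's own planning values.

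**Inputs**
- Means (SD) from the Registry Sample Size Example in section 9.1.2, RUSH2A overall: visual acuity (VA) 77.9 (11.7) letters, V_tot 27.8 (23.7) dB-sr, EZ area 3.6 (5.6) mm². The protocol describes these as "Assumptions based on Mean (standard deviation) of RUSH2A baseline" values.
- Inter-eye correlation r = 0.8, the planning value in section 9.1.1, which also says that the "correlation between eyes (inter-eye correlation) for each outcome measure is not known". It is varied from 0.5 to 0.9 below.
- N = 50, from the same example; 20 and 100 are also used.
- VA SD from 5 to 20, the range of Table 9-2.
- Assumptions that are not protocol figures: normal data, and true differences of 3 letters, 6.1 dB-sr and 1.4 mm², sizes at which a centred test has roughly 80% power at N = 50.

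**Step 1: identity.** For D = a + bM, least squares gives a = D̄ − b·M̄. So a = D̄ only if b = 0 or M̄ = 0, and the second is what centring achieves.

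**Step 2: non-zero slope.** With a true mean difference of 0 and slope 0.1, the raw intercept is
- VA: −0.1 × 77.9 = −7.79 letters
- V_tot: −0.1 × 27.8 = −2.78 dB-sr
- EZ area: −0.1 × 3.6 = −0.36 mm²

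Simulated for VA at N = 50 (3,000 replicates), the raw intercept test rejects in 18% of runs at slope 0.1 and 53% at slope 0.2; the centred test rejects in about 6%. These slopes arise when one eye's SD exceeds the other's by roughly 10% and 20%; they are illustrations, not predictions. In reverse, a true difference of 3 letters with slope 3/77.9 = 0.0385 gives an intercept of exactly 0: the raw test rejects in 5% of runs and the centred test in 81%.

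**Step 3: precision with zero slope.** SD_M = SD·√((1+r)/2), SD_D = SD·√(2(1−r)), SE(D̄) = SD_D/√N, and SE(a) = SE(D̄)·√(1 + (mean/SD_M)²). At N = 50:

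| Measure | SD_M | SD_D | SE(D̄) | Ratio | SE(a) |
|---|---|---|---|---|---|
| VA | 11.10 | 7.40 | 1.05 | √(1+(77.9/11.10)²) = 7.09 | 7.42 |
| V_tot | 22.48 | 14.99 | 2.12 | √(1+(27.8/22.48)²) = 1.59 | 3.37 |
| EZ area | 5.31 | 3.54 | 0.50 | √(1+(3.6/5.31)²) = 1.21 | 0.61 |

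**Step 4: power with zero slope.** Simulation, 100,000 replicates per scenario, two-sided 0.05, N = 50, r = 0.8:

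| Measure, true difference | Raw intercept | Centred intercept | Joint F (2 df) |
|---|---|---|---|
| VA, 3 letters | 7% | 80% | 70% |
| V_tot, 6.1 dB-sr | 42% | 81% | 71% |
| EZ area, 1.4 mm² | 61% | 78% | 68% |

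A paired t-test agrees with the centred intercept within 0.3 points. For VA, the difference detectable with 80% power is about 22 letters raw and 3.0 letters paired.

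**Step 5: sensitivity for VA, 3 letters (raw against centred).** For VA, SE(a) is close to mean × 2√((1−r)/(1+r))/√N, so the SD nearly cancels and raw power stays low throughout.
- N = 50, SD 5: 7% against 100%. SD 20: 7% against 37%.
- SD 11.7, N = 20: 6% against 41%. N = 100: 9% against 98%.
- SD 11.7, N = 50, r from 0.5 to 0.9: 6–9% against 43–98%.
- SD 20, N = 50, assumed mean 40 for a gene with more low-vision participants (Vision Cohort 2 in section 2.2 covers an "ETDRS letter score of 19-53 (approximate Snellen equivalent 20/100 to 20/400"): 11% against 37%, SE ratio 2.3.

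With SD 20 the centred test is itself underpowered for 3 letters.

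**The case against.** The strongest reply is that the parenthesis states the intended quantity and a centred fit delivers exactly that, so the protocol is only silent on a coding detail that an analysis plan would settle. The regression clause also does not name its regressor, and the wording can be read as one joint test of intercept and slope, which does not depend on centring. The power figures take zero slope, the case in which the label is right in expectation, so they measure lost precision and not mislabelling. The normal model is crude: it puts about 25% of simulated EZ means and about 11% of V_tot means below 0. Finally, no hypothesis about a left-right mean difference was planned or powered.

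Part of this stands. An analyst may well centre, and the joint F test is a valid reading with 70% power for VA. The EZ and V_tot power figures are illustrative only, although the SE ratios do not need normality. The exploratory status limits the consequence.

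The rest does not remove the problem. The regressor follows from the difference-versus-mean plot in the same sentence. The protocol is also not merely silent: it equates the intercept with the mean difference in a model whose slope it tests, so it cannot take that slope as 0. A joint test would not isolate the quantity in the parenthesis. Zero slope is also the case kindest to the protocol's wording; step 2 shows the test misleading in both directions once a slope exists.

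**Conclusion.** The point holds. As written, the intercept test addresses the inter-eye difference at a mean of 0, not the overall mean difference. The consequence arises only if the mean is left uncentred and intercept and slope are tested separately. In that case the visual acuity test is close to uninformative: 7% power against 80% for an assumed 3 letters at N = 50, with raw power staying at 6–11% over the variations tried. The loss is moderate for V_tot and small for EZ area. These sizes rest on RUSH2A values, an assumed inter-eye correlation and normal data; the values for individual genes are unknown.

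The reach is small. This is one exploratory Registry analysis, supported by scatterplots, Bland-Altman plots and the intraclass correlation. Sample size and the Natural History Study symmetry analysis are not affected. It is a wording correction worth making.

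**What to change.** In section 9.2.1, or in the statistical analysis plan, state that the inter-eye mean is centred at its sample mean before the regression is fitted; the intercept is then exactly the mean inter-eye difference. Alternatively, test the mean difference with a paired t-test and use the regression for the slope only. Either is one phrase, can be applied at analysis, needs no new data and loses none.
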